## 9.2 Statistical Analysis Plan

Primary analyses will be performed as follows. Within each race-based cohort, the ribociclib exposure which measured by ribociclib AUC will be summarized by median [Interquartile range, IQR], and two-sample t-test if normality holds or Wilcoxon-Mann-Whitney test will be used to compare AUC between CYP3A5 poor metabolizers and CYP3A5 intermediate or normal metabolizer in each independent race-based cohort. Secondary analyses will be performed as follows. Descriptive statistics will be used to characterize the data profile, frequency and percentages for categorical variables, and mean (SD) or median [IQR] for continuous variables based on the data normalization. Multiple regression will be used to identify variables associated with ribociclib AUC. To best account for any factor that may affect ribociclib exposure, covariates to be assessed include CYP3A5 metabolism status, renal function, liver function, age, race, weight, sex, among others. Any covariates with  $P < 0.2$  on univariate analysis will enter the stepwise multiple linear regression model, with  $P < 0.05$  considered statistically significant. This methodology will also be used to assess a change in absolute neutrophil count and QTc as the outcome variable. Depending on data distribution, a two-sample t-test or Wilcoxon-Mann-Whitney test will be used for 1) a change (baseline and C1D8-C1D16) in continuous variables (e.g., QTc, absolute neutrophil count) between CYP3A5 poor metabolizers and CYP3A5 intermediate or normal metabolizers, 2) to check the association between a continuous variables and categorical risk factors. Pearson correlation coefficient or Spearman correlation coefficient will be calculated to measure the association between two continuous variables. Fisher's exact test will be used for checking the association between two categorical variables. AEs will be assessed with descriptive statistics and univariate logistic regression will assess the occurrence of specific AEs with pharmacokinetic properties (e.g., AUC,  $C_{max}$ ). The approach from the linear regressions will be adapted to logistic regression to identify covariates associated with the occurrence of grade III or IV neutropenia.

Descriptive analysis of the PRO-CTCAE adverse event log to determine frequency of adverse events by race and by CYP3A5 genotype.

Descriptive statistics will be used to describe the patients reported outcomes in the survey (see Appendices). As an exploratory analysis, multiple regressions will be used to assess the relationship between patients reported outcomes and other covariates (mentioned above) with ribociclib AUC.

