### 2.2 Primary Endpoint

Ribociclib AUC (visit between days 8-16 of cycle 1) CYP3A5 poor metabolizers and CYP3A5 intermediate or normal metabolizers.

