## **3.3 Inclusion Criteria**

Patients must meet all the following inclusion criteria to be eligible for enrollment in the study:

- Signed informed consent must be obtained prior to any screening procedures that are not standard of care.
- Female  $\geq 18$  years old at the time of informed consent.
- Those who self-identify as African American or Black are eligible for that respective cohort
- Those who self-identify as non-Hispanic White are eligible for that respective cohort
- Postmenopausal or premenopausal. Patient has a known menopausal status at the time of the informed consent form signature. The patient is considered postmenopausal if: i) she has had prior bilateral oophorectomy; ii) is age  $\geq 60$  years; iii) is age  $<60$  years and has had amenorrhea for 12 or more months (in the absence of chemotherapy, tamoxifen, toremifene, or ovarian suppression) and follicle-stimulating hormone (FSH) and estradiol in the postmenopausal range per local normal ranges. All other patients who do not meet the criteria for postmenopausal status are considered premenopausal and will receive a luteinizing hormone-releasing hormone (LHRH) agonist (i.e., goserelin, leuprolide) for ovarian suppression
- Each race-based cohort has a predetermined number of patients with each CYP3A5 phenotype per the sample size calculation (section 9.1). Patients will be screen for CYP3A5 according to section 3.6.1.

- African American or Black
  - At least 3 participants who are CYP3A5 poor metabolizers
  - No more than 15 participants who are CYP3A5 intermediate or normal metabolizers
- Non-Hispanic White
  - At least 3 participants who are CYP3A5 intermediate or normal metabolizers
  - No more than 15 participants who are CYP3A5 poor metabolizers
- Patient has advanced (loco-regionally recurrent or metastatic) breast cancer not amenable to curative therapy
- Treated, stable and asymptomatic brain metastases are permitted
- ECOG performance status 0-3
- Documentation of estrogen receptor (ER) positive and/or progesterone receptor (PR) positive tumor ( $\geq 1\%$  positive stained cells) based on most recent tumor biopsy (discuss with the Principal Investigator if results in different biopsies are discordant in terms of hormone receptor positivity) utilizing an assay consistent with local standards.

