## **9 Data Analysis and Statistical Methods**

### **9.1 Sample Size, Accrual and, Study Duration**

This study is powered to assess the primary outcome (ribociclib in CYP3A5 poor metabolizers vs. CYP3A5 intermediate or normal metabolizers) independently within each race-based cohort. The pharmacokinetic study used to inform the FDA's decision to suggest alternative dosing for patients prescribed a strong CYP3A inhibitor (ritonavir) exhibited a 3.2-fold increase in AUC (15). Genotype may have a lower effect, but the extent of the effect is unclear. We will aim to detect a minimum clinically meaningful change: 2-fold change in AUC, which is less than the fold changes seen in the ritonavir CYP3A drug interaction pharmacokinetic study. In the meantime, data from the same pharmacokinetic study showed the standard deviation of AUC fold change (in  $\log_2$  scale) was 0.56. Given that the groups in our study are considered similar, to be conservative, we used the standard deviation of 0.75 in our calculation.

Allelic frequencies for CYP3A5 are provided from CPIC and PharmGKB and translated to phenotypes via the Hardy-Weinberg equation (32). Based on these frequencies (normal metabolism: 35%; intermediate metabolism: 48%; poor metabolism: 16%), a sample size of 18 would provide 80% power at an  $\alpha=0.05$  to detect a 2-fold change in AUC between CYP3A5 poor metabolizers vs. CYP3A5 expressors (i.e., CYP3A5 intermediate or normal metabolism) in African Americans/Blacks. Based on the allelic frequencies for Non-Hispanic Whites (normal metabolism: 0.6%; intermediate metabolism: 14.7%; poor metabolism: 84.6%), a sample size of 18 would also provide 80% power at an  $\alpha=0.05$  to detect a 2-fold change in AUC between CYP3A5 poor metabolizers vs. CYP3A5 expressors (i.e., CYP3A5 intermediate or normal metabolism).

Thus, an overall sample size of 36 would provide adequate power to independently test the primary outcome in the two race-based cohorts.

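### Section 9.1 sizes each cohort on a fold change in AUC on the log2 scale, but Section 9.2 states no scale for the primary test, lets an undefined normality check choose it, and plans no ratio with a confidence interval.

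*Combined protocol and SAP*

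**What the plan says.** Section 9.1 fixes the target: "We will aim to detect a minimum clinically meaningful change: 2-fold change in AUC". For variability it says that "data from the same pharmacokinetic study showed the standard deviation of AUC fold change" was 0.56 and labels that figure as log2. It then raises the figure: "Given that the groups in our study are considered similar, to be conservative, we used the standard deviation of 0.75 in our calculation". The scale of 0.75 is not repeated but follows from the context. Each cohort has 18 patients, with a claimed 80% power at alpha 0.05.

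Section 2.2 gives the primary endpoint as "Ribociclib AUC (visit between days 8-16 of cycle 1") by CYP3A5 group, with no scale.

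Section 9.2 says AUC "will be summarized by median [Interquartile range, IQR"] and that a "two-sample t-test if normality holds or Wilcoxon-Mann-Whitney test will be used to compare AUC between CYP3A5 poor metabolizers" and intermediate or normal metabolizers within each cohort. It does not say how normality is judged, at what level, on which scale, or by group or pooled. It does not say whether the t-test assumes equal variances. The rest of 9.2 and Section 9.3 add no ratio and no confidence interval for the primary comparison.

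Section 3.3 sets the minimum size of the smaller group. In the African American/Black cohort it is "At least 3 participants who are CYP3A5 poor metabolizers". In the Non-Hispanic White cohort it is "At least 3 participants who are CYP3A5 intermediate or normal metabolizers". The larger group is capped at 15 in each.

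**The concern.** A 2-fold change with a log2 SD is a hypothesis about a ratio, so the matching analysis is a difference in mean log2 AUC. Section 9.2 does not commit to it. That matters here for two reasons.

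First, the cohorts are mirror images. Under the hypothesis in Section 1.5, poor metabolizers have the higher exposure. The small group is therefore the high-AUC group in the African American/Black cohort and the low-AUC group in the Non-Hispanic White cohort. On raw AUC the high group also has the larger spread, so a raw-scale t-test treats the same 2-fold effect differently in the two cohorts. On log2 AUC it does not.

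Second, nothing planned estimates the fold change with its uncertainty. With about 3 patients in one group, two medians and a p-value cannot show whether a 2-fold difference is supported or excluded.

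**Working it through.** **Inputs.** From 9.1: effect log2(2) = 1; SD 0.75 (used) and 0.56 (source); alpha 0.05, taken as two-sided because 9.1 does not say. Group sizes 3 and 15 come from 3.3. They agree with the frequencies in 9.1: 0.16 × 18 = 2.9 poor metabolizers, and (0.006 + 0.147) × 18 = 2.8 expressors.

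**The plan's own figure.** For an equal-variance t-test on log2 AUC:
- SE = SD × √(1/3 + 1/15) = SD × 0.632, which is 0.474 at SD 0.75 and 0.354 at SD 0.56.
- Noncentrality = 1/SE = 2.108 and 2.823.
- Noncentral t on 16 df (critical value 2.120): power 50.8% and 75.5%.
- Normal approximation: 55.9% and 80.6%.

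The stated 80% is thus not reproduced at SD 0.75 with a 3:15 split. That is a separate problem; the 50.8% and 75.5% serve here as reference values.

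**Effect of the open choices.** Log2 AUC was simulated as normal with equal SDs, and the small group was shifted by +1 (African American/Black) or −1 (Non-Hispanic White). The normality check is assumed to be Shapiro-Wilk at 0.05 in each group. If both groups pass, the t-test is used; otherwise the exact Wilcoxon-Mann-Whitney test. Each row uses at least 10,000 cohorts (Monte Carlo SE about 0.5 points or less). The unchecked log2 equal-variance row agrees with the analytic values.

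| Rule | SD 0.75: AA/Black | SD 0.75: NHW | SD 0.56: AA/Black | SD 0.56: NHW |
|---|---|---|---|---|
| Raw AUC, check, equal-variance | 54% | 36% | 78% | 62% |
| Raw AUC, check, Welch | 26% | 53% | 38% | 72% |
| Log2 AUC, check, equal-variance | 50% | 51% | 75% | 75% |
| Log2 AUC, no check, equal-variance | 51% | 51% | 75.5% | 75.5% |
| Log2 AUC, no check, Welch | 36% | 36% | 52% | 51% |
| Exact Wilcoxon alone | 42% | 42% | 66% | 66% |

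The components separate as follows.
- *Scale* (equal-variance, SD 0.75): moving from raw to log2 AUC changes power from 54% to 50–51% in one cohort (3 to 4 points down) and from 36% to 51% in the other (15 up). At SD 0.56 the changes are 78 to 75.5 and 62 to 75.5.
- *Normality check*: on log2 AUC it costs about 1 point or less. On raw AUC it passes in only about 55% of cohorts at SD 0.75 and 69% at SD 0.56, so the test actually used is largely a matter of chance.
- *t-test variant*: on raw AUC, Welch instead of equal-variance lowers African American/Black power by 54 − 26 = 28 points at SD 0.75 and 78 − 38 = 40 at SD 0.56. On log2 AUC it costs 51 − 36 = 15 and about 23 to 24.

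**Type I error on log2 AUC, 3 against 15.** With equal SDs: 5% (equal-variance), about 7% (Welch), about 4% (exact Wilcoxon). With unequal SDs, which are assumptions (small group / large group), the equal-variance test gives about 10% at 0.75/0.56 and about 1% at 0.5/0.8; Welch stays at about 6–7%. The raw-AUC rule with the equal-variance test is equally exposed (10.4% and 1.3%).

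**The missing interval.** Half-width = 2.120 × SE = 1.006 log2 units at SD 0.75, a factor of 2.01, and 0.751 at SD 0.56, a factor of 1.68. An observed ratio of 2.0 would carry a 95% CI of about 1.0 to 4.0, or 1.2 to 3.4.

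**The case against.** Section 9.2 does not prescribe untransformed AUC; it is silent. Since 9.1 speaks of a fold change and a log2 SD, an analyst could reasonably take log2 AUC as the scale on which normality is to hold. On that reading the cohorts have equal power and the check does almost no harm. The Wilcoxon-Mann-Whitney branch is the same on either scale. This stands: the gap is an unstated scale, and the imbalance arises only if raw AUC is used.

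A reader might also infer that the scale mismatch costs 28 or even 40 points of power. It does not. Those gaps lie between the equal-variance and Welch tests within the raw-scale reading. The scale itself accounts for about 4 points in one cohort and 15 in the other at SD 0.75.

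Nor do the calculations show a false-positive problem caused by the scale. With equal log2 SDs, type I error is near 5% for the equal-variance test on either scale, and the weakness under unequal SDs exists on both.

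The sizes rest on assumptions: log-normal AUC, the form of the check, and exactly 3 against 15 although 3.3 sets 3 as a minimum. In addition, 9.1 describes 0.56 as the SD of a fold change in a drug-interaction study, and the documents do not show that it is the between-patient SD within a phenotype group.

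Finally, 9.2 plans a secondary regression of AUC on CYP3A5 status and other covariates. It does not fill the gap: its scale is also unstated, its covariates are chosen stepwise by p-value, and it is not the primary comparison.

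**Conclusion.** The point holds as a mismatch between sizing and analysis and as a gap in prespecification. Section 9.1 defines the question as a ratio on the log2 scale, while 9.2 leaves the scale, the normality criterion and the t-test variant open and plans no ratio with an interval. Under the assumptions above and at SD 0.75, a literal raw-AUC reading with the equal-variance test gives about 54% and 36% power in the two cohorts, against about 51% in both on log2 AUC. At SD 0.56 the figures are 78% and 62% against 75.5% in both. The variant is a separate open choice with a larger effect. The documents do not support saying that 9.2 mandates raw AUC, or that the primary test is invalid. The sponsor should correct this before the data are analysed; confidence in the sizes is moderate because they depend on the assumed distribution and check.

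**What to change.** In Section 9.2, make the primary analysis in each cohort a two-sided equal-variance t-test on log2(AUC), with no normality pre-test. Equal variance matches the single SD in 9.1. Report the geometric mean ratio (poor over intermediate-or-normal) with its 95% CI, read against the 2-fold reference. State log2 AUC as the analysis scale in 2.2 as well.

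Report the Welch test and the exact Wilcoxon-Mann-Whitney test as sensitivity analyses, and keep median [IQR] as description. State that the type I error of the equal-variance test departs from 5% if the group SDs differ, with the 10% and 1% scenarios above as examples.

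The change is wording only and needs no more patients. Against the raw-scale equal-variance reading at SD 0.75, it gives up about 4 points of power in the African American/Black cohort and gains about 15 in the Non-Hispanic White cohort. It does not bring power to the 80% stated in 9.1, which needs its own correction.

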## 1.5 Study Rationale and Purpose

There is an unmet need to evaluate the genomic characteristics and their effect on drug metabolism and toxicities, especially in racial and ethnic minorities. This prospective cohort study aims to determine the impact of CYP3A in ribociclib metabolism.

Ribociclib is metabolized by CYP3A and the FDA recommends avoidance of CYP3A inhibitors or dose adjustments to compensate for altered ribociclib metabolism (section 1.2.2). Based on drug interaction data (section 1.2.2), a reduction in CYP3A activity can lead to clinically relevant changes in ribociclib exposure. Higher ribociclib exposure is known to be associated with toxicities (e.g., neutropenia, prolonged QTc interval) and decreased exposure can potentially lead to loss of efficacy (14).

Genetic variation in CYP3A, and specifically in CYP3A5, may be associated with altered ribociclib exposure but this has not been studied. Separate studies in African Americans/Black and Non-Hispanic White patients are justified given allelic frequencies and the potential for factors (e.g., CYP3A4) that may confound the association between CYP3A5 and ribociclib exposure.

Due to underrepresentation in clinical trials and race-based differences in CYP3A5 expression, African Americans/Blacks may be at particular risk of atypical ribociclib exposure. However, the dearth of pharmacokinetic evidence for ribociclib use in African Americans/Blacks patients make clinical predictions difficult. It is reasonable to suggest that African Americans/Blacks may be *either* 1) more dependent on metabolic activity from CYP3A5 and thus CYP3A5 poor metabolism may lead to increase ribociclib exposure and possibly toxicity or 2) normal CYP3A5 metabolizers have increased metabolic activity compared to the “average” White patient, which results in lower ribociclib exposure and a lack of efficacy. In order to predict which scenario is more plausible, it is critical to first understand if differences in ribociclib pharmacokinetics are associated with CYP3A5 metabolizer status. **We hypothesize that patients treated with ribociclib who are CYP3A5 poor metabolizers may be exposed to higher levels of ribociclib than CYP3A5 intermediate or normal metabolizers.** These differences can then inform the plausible clinical risk.

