## 2. Study Objectives and Endpoints

### 2.1 Primary Objective

To compare the pharmacokinetics of ribociclib at steady-state between CYP3A5 poor metabolizers and CYP3A5 intermediate or normal metabolizers in each independent race-based cohort of women with advance breast cancer.

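### Two within-cohort tests will often split by chance, and section 9.2 plans no ratio with a CI, no CYP3A5-by-cohort estimate and no fixed cohort-adjusted model to interpret the split

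*Combined protocol and SAP*

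**What the plan says.** Section 2.1 sets the primary objective as a comparison of CYP3A5 poor metabolizers with intermediate or normal metabolizers (expressors) "in each independent race-based cohort of women with advance breast cancer". Section 9.1 powers it "independently within each race-based cohort". Section 9.2 summarises AUC by median and interquartile range and states that a two-sample t-test or a Wilcoxon-Mann-Whitney test "will be used to compare AUC between CYP3A5 poor metabolizers and CYP3A5 intermediate or normal metabolizer in each independent race-based cohort". It plans no poor/expressor ratio, no confidence interval and no contrast of the CYP3A5 effect between cohorts.

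The cohorts are pooled in the secondary multiple regression of AUC, because race is one of its candidate covariates. CYP3A5 status and race are listed there as separate terms. Candidates must pass a univariate screen at P<0.2 and then a stepwise procedure. A further exploratory regression relates patient-reported outcomes and the same covariates to AUC. Neither names a product term.

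Section 1.5 suggests, as one of two scenarios, that Black patients may be "more dependent on metabolic activity from CYP3A5 and thus CYP3A5 poor metabolism may lead to increase ribociclib exposure". It justifies separate cohorts by allele frequencies and by factors such as CYP3A4 that may confound the association.

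**The concern.** Greater dependence on CYP3A5 in one cohort is a statement about effect modification: the poor/expressor ratio would be larger there. The plan offers nothing that estimates this. What it will produce is two p-values, and each rests on a smallest group that may be only three women. If one is below 0.05 and the other is not, readers of a race-focused rationale could take the split as a race-specific CYP3A5 effect, although a difference in significance is not a test of a difference.

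The pooled regression does not close the gap. It has no product term, and its selection rules may remove race. By design most poor metabolizers are White and most expressors are Black. A CYP3A5 coefficient without cohort in the model can therefore carry part of any other difference in exposure between the cohorts.

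**Working it through.** **Inputs.** From section 9.1: "We will aim to detect a minimum clinically meaningful change: 2-fold change in AUC", which is 1 on the log2 scale; "we used the standard deviation of 0.75 in our calculation"; a log2 SD of 0.56 in the cited drug-interaction study; alpha 0.05; stated power 80%; 18 women per cohort. From section 3.3: at least 3 women in the rarer phenotype group and at most 15 in the commoner one. Assumptions: exactly 3:15 in both cohorts, two-sided tests (sidedness is not stated), normal log AUC with equal SDs, and no non-evaluable patients.

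**1. The plan's own power.** SE = 0.75 × √(1/3 + 1/15) = 0.75 × √0.4 = 0.474. The noncentrality is 1/0.474 = 2.11 on 16 df. Power is 50.8% (55.9% by the normal approximation), not 80%. With SD 0.56 it is 75.5% (80.6% normal). With SD 0.75 and a 9:9 split the normal approximation gives 80.7%. That discrepancy is a separate matter. Here it only means that the split rate must be shown over a range of power.

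**2. Chance of a split verdict.** For two independent cohorts with the same true effect and power p, P(exactly one significant) = 2p(1 − p).

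| Basis, 2-fold effect in both | p | Exactly one significant |
|---|---|---|
| Stated power | 0.800 | 2 × 0.800 × 0.200 = 32% |
| SD 0.56 | 0.755 | 2 × 0.755 × 0.245 = 37% |
| SD 0.75 | 0.508 | 2 × 0.508 × 0.492 = 50% |

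The rate depends on the common effect. At SD 0.75 it is 33% for 1.5-fold, 38% for 2.5-fold and 16% for 3.2-fold. At SD 0.56 the corresponding rates are 45%, 12% and 1%.

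In 200,000 simulated trials with identical 2-fold effects and SD 0.75, the tests split in 50.0%. An interaction test declared a difference in 5.0% of all trials, and in 9% of those that split.

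**3. What the same 36 women can estimate (SD 0.75).** The 95% CI factor is 2^(t × SE).

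| Estimate | SE (log2) | df | 95% CI |
|---|---|---|---|
| Ratio in one cohort | 0.75 × √0.4 = 0.474 | 16 | ×/÷2.01 |
| Cohort-adjusted common ratio | 0.75 × √(0.4/2) = 0.335 | 33 | ×/÷1.60 |
| Ratio of ratios (interaction) | 0.75 × √(2 × 0.4) = 0.671 | 32 | ×/÷2.58 |

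The common ratio has 82% power for a 2-fold effect (97% at SD 0.56). The interaction has 30% power for a 2-fold difference in effect and reaches 80% only at about 3.8-fold. At SD 0.56 its CI factor is 2.03, its power for 2-fold is 49%, and 80% power needs 2.7-fold.

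**4. Dropping race from the pooled regression.** At 3:15 and 15:3 there are 18 poor metabolizers, 15 of them White (83%), and 18 expressors, 3 of them White (17%). The correlation between the two indicators is (15 × 15 − 3 × 3)/(18 × 18) = 216/324 = 0.67. With cohort out of the model, the CYP3A5 coefficient takes up 15/18 − 3/18 = 0.67 of any White-minus-Black difference in log AUC that arises from other causes.

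**The case against.** The strongest case is that the plan does what it sets out to do. The primary objective is within-cohort, and no listed objective or endpoint asks whether the CYP3A5 effect differs by race. The scenarios in section 1.5 are motivation. Its highlighted hypothesis compares poor metabolizers with the others without a race modifier, and its hypothesis about race concerns AUC and toxicity. At n = 36 an interaction is badly underpowered, so leaving out a test of it is defensible. A common ratio also assumes similar effects, which these data could not verify.

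Much of this stands, and it rules out three stronger readings.

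- A reader might infer that the two tests fail to answer the primary question. They do answer it as written.
- A reader might infer that the plan will treat a split as a race difference. No section says that the p-values will be compared. The calculation shows how often the tests split, not how a split will be read.
- A reader might infer that the cohorts are never combined. The secondary regression pools them, and if both terms survive selection it gives an adjusted CYP3A5 estimate.

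What the objection does not remove is the interpretive gap. Section 1.5 raises effect modification, the plan offers no estimate of it, and the pooled estimate depends on what selection retains. Low interaction power is a reason to report the estimate with its interval and to rule out inference from two p-values.

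**Conclusion.** The point holds as a gap in interpretation and estimation. The two within-cohort tests are sound as the answer to the primary objective. With the same true 2-fold effect in both cohorts, a third to a half of trials would show significance in exactly one: 32% at the stated power, 37% at SD 0.56, 50% at SD 0.75. The plan has no ratio with a CI and no interaction estimate to put such a split in context, and its pooled model may omit the variable needed to keep the CYP3A5 estimate unconfounded.

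The figures rest on the assumptions listed with the inputs. The Wilcoxon option was not calculated. The split rate is lower when the common effect is large relative to the SD. The 50% figure depends on the SD and group sizes in section 9.1 and section 3.3 giving less than the stated power, but the 32% figure does not.

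**What to change.** Keep both within-cohort comparisons unchanged and add to section 9.2:

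- In each cohort, the poor/expressor geometric mean ratio of AUC with its 95% CI.
- One pre-specified linear model of log AUC (section 9.1 already works on the log2 scale) that always contains cohort and CYP3A5 group, outside any screening or stepwise step. Report the cohort-adjusted common ratio with CI as a supportive estimate.
- From the same model with a cohort-by-CYP3A5 term, the ratio of the two cohort ratios with CI.
- A statement that a cohort difference will be claimed only from that interaction estimate, and that a split in significance is not evidence of a race difference. It should add that the interaction is estimated and not powered (about 30% for a 2-fold difference in effect at SD 0.75), so a non-significant interaction does not show equal effects.

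This costs one paragraph and no new patients, samples or data. The drawbacks are a wide interaction interval and a common ratio that assumes similar effects in both cohorts, which is why it should stay supportive.

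### The secondary AUC regression leaves both CYP3A5 status and race to stepwise selection although they are correlated by up to 0.67; forcing both in is a minor, low-cost improvement

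*Combined protocol and SAP*

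**What the plan says.** The primary analysis in section 9.2 compares AUC by CYP3A5 phenotype separately within each race cohort. Among the secondary analyses, the section adds: "Multiple regression will be used to identify variables associated with ribociclib AUC". It lists the candidates: "covariates to be assessed include CYP3A5 metabolism status, renal function, liver function, age, race, weight, sex, among others". Those with P<0.2 "on univariate analysis will enter the stepwise multiple linear regression model", and P<0.05 counts as significant.

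The rule is reused: "This methodology will also be used to assess a change in absolute neutrophil count and QTc as the outcome variable". For grade III or IV neutropenia, "The approach from the linear regressions will be adapted to logistic regression".

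No term is forced into any of these models, and the direction of the stepwise procedure is not given. Pooling of the two cohorts is not stated, but it is implied, because race cannot be a covariate within a single race cohort.

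Two other places link CYP3A5 status to race:

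- **Section 9.1** gives 16% poor metabolizers among African American/Black patients. For Non-Hispanic White patients it gives (in per cent) "normal metabolism: 0.6%; intermediate metabolism: 14.7%; poor metabolism: 84.6".
- **Section 3.3** requires at least 3 poor metabolizers among the 18 African American/Black patients and "No more than 15 participants who are CYP3A5 intermediate or normal metabolizers". The quotas for the Non-Hispanic White cohort are the mirror image.

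**The concern.** Most patients in one cohort are poor metabolizers and most in the other are not, so the two variables carry overlapping information. A univariate screen followed by stepwise selection will often keep only one of them. If race affects exposure by a route other than CYP3A5, the retained term then carries part of the omitted one.

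Section 1.5 allows for such a route. It justifies separate cohorts partly by "the potential for factors (e.g., CYP3A4) that may confound the association between CYP3A5 and ribociclib exposure". The pooled model brings back the confounding that the cohort design avoids.

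What is at stake is the model's stated purpose of identifying associated variables. CYP3A5 could be named when it has no effect, or dropped when it has one. If the fitted coefficient is also reported, its size and interval can be wrong.

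**Working it through.** **Plan figures.** The plan gives no correlation and no operating characteristics for this regression. The 80% power in section 9.1 is for the within-cohort test and is not used here.

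**Inputs from the documents.** 18 patients per cohort; phenotype limits of 3 and 15 (section 3.3); a 2-fold change, which is 1.0 on the log2 scale, and SD 0.75 log2 (section 9.1); P<0.2 screen and P<0.05 retention (section 9.2).

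**Assumptions.** These two covariates only; a common CYP3A5 effect in both cohorts; a race effect (African American/Black minus Non-Hispanic White at equal CYP3A5 status) from -0.75 to +0.75 log2. For scale, 0.25, 0.5 and 0.75 log2 are 1.19-, 1.41- and 1.68-fold.

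**Correlation.** With k minority-phenotype patients in each cohort it is (18-2k)/18:

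- k=3: 12/18 = 0.67
- k=4: 10/18 = 0.56
- k=5: 8/18 = 0.44

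The frequencies alone would give about 0.846-0.16 = 0.69. So the allele frequencies create the correlation, and the quotas cap it.

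**Absorption.** A model with CYP3A5 alone estimates, on average, the CYP3A5 effect minus 0.667 times the race effect at 3/15. For a true value of 1.0:

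- race -0.5: 1+0.333 = 1.33
- race +0.5: 1-0.333 = 0.67
- race +0.75: 1-0.50 = 0.50

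**Forced model.** The SE at 3/15 is 0.75 x sqrt((1/3+1/15)/2) = 0.335. With 33 df, power is 82-83% for 1.0 log2.

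**Selection rule at 3/15, true CYP3A5 effect 1.0 log2.** At least 40,000 simulated trials per row; ranges cover backward and forward selection. Coverage is that of a conventional 95% CI for the retained coefficient.

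| Race effect | CYP3A5 kept | Mean retained estimate | Coverage |
|---|---|---|---|
| -0.75 | 83-84% | 1.24 | 77% |
| -0.5 | 86% | 1.25 | about 80% |
| -0.25 | 90% | 1.16 | 91% |
| 0 | 93% | 1.02 | 96% |
| +0.25 | 88-89% | 0.89 | 96% |
| +0.5 | about 72% | 0.78-0.79 | 94% |
| +0.75 | 44-46% | 0.72-0.75 | 92% |
| Any, both forced | 82-83% | 1.00 | 95% |

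At race -0.5 both terms survive in 19% of trials; at +0.5 in under 1%.

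**Less extreme splits.**

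- 4/14: at race -0.5, kept in 92% (mean 1.17, coverage 87%); at +0.5, 78-80% (0.82-0.83, 96%). Forced: 90%.
- 5/13: at race -0.5, 95% (1.12, 91%); at +0.5, 84-87% (0.88, 97%). Forced: 93-94%.

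**No CYP3A5 effect.** At 3/15, CYP3A5 is selected in about 4% (race 0), 6.5% (0.25 in size), 9.5-9.6% (0.5) and about 9% (0.75). The maximum is 7.6% at 4/14 and 6.2% at 5/13. Forced, it is 5%.

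**Neutropenia logistic model.** All outcome tables were enumerated exactly, with likelihood-ratio tests, backward elimination, no CYP3A5 effect and an assumed event rate of 30-50%. At 3/15 the mirror-image layout makes the two P values tie in the elimination step in 14-17% of trials at race odds ratios of 3-5. False selection therefore depends on how ties are handled:

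- ties drop CYP3A5: 5.8-6.5%
- ties split: 9.5-11.3%
- ties drop race: 13.0-16.7%
- both forced: 7.4-9.7%

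At odds ratio 2 the figures are 7.4-8.0% with ties split and 7.0-7.6% forced. At 5/13 (odds ratio 3-5) they are 6.8-7.5% and 6.3-6.8%.

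No calculation was made for the ANC and QTc models.

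**The case against.** **The race effect is unquantified.** This stands. With none, the existing rule is nearly unbiased and has more power. Section 1.5 also attributes the expected race difference in AUC to CYP3A variants. That does not remove the point, because CYP3A4 is one of those variants and is outside the CYP3A5 term. The largest assumed effect (1.68-fold) approaches the 1.9-fold change that section 1.2.2 gives for a moderate CYP3A inhibitor, so it is an upper scenario.

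**The existing rule often finds CYP3A5 at least as often.** True for race effects from -0.75 to +0.25. For negative race effects, though, the higher rate comes with an inflated coefficient.

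**No estimate is promised.** Section 9.2 aims to identify variables; it specifies no CYP3A5 ratio or CI. The direct consequence is therefore wrong selection. The bias and coverage figures matter only if the coefficient is reported.

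**Other analyses protect the main question.** For AUC, the primary within-cohort tests already do so. For QTc and ANC change, section 9.2 also plans a direct comparison by CYP3A5 status, without saying how the cohorts are handled. Exploratory endpoints 5 and 6 and section 9.3 look at CYP3A4 and the Duffy antigen, but force nothing into the section 9.2 models.

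**Two stronger readings are tempting.** A reader might infer that the primary result is compromised. It is not, because race is constant within each primary comparison. A reader might also infer that the harm is greatest for neutropenia, which has no planned within-cohort counterpart. The enumeration does not support this: the forced model also exceeds 5%, and the gain from forcing is small and depends on tie handling.

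**Conclusion.** The point holds for the secondary AUC regression as a minor one. At 3/15, with a true 2-fold CYP3A5 effect, the share of trials keeping CYP3A5 ranges from 93% with no race effect down to about 46% at +0.75 log2, while forcing both terms holds 82-83% throughout. Marked under-coverage needs a negative race effect and is worst at 3/15. The worst false selection is about 9.6%, roughly twice the forced rate.

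All of this rests on an assumed race effect, SD 0.75 log2, a two-covariate model and splits near the quota limit; it shrinks at 4/14 and 5/13. For neutropenia the documents and the arithmetic support little gain from forcing. For ANC and QTc the argument is one of consistency only.

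**What to change.** In section 9.2:

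- State that the secondary AUC model pools both cohorts, fit it on log2 AUC, and force in CYP3A5 status and race cohort. Apply selection only to the other covariates.
- Use the same two forced terms in the ANC and QTc change models for consistency.
- For grade III/IV neutropenia, forcing both is optional. At a 30-50% event rate the smaller outcome class has a median of 11-16 patients, about 5-8 per forced term. Label the result exploratory.
- Delete sex from the list, since only women are eligible. This is a list error and adds no weight to the point.
- Report the pooled CYP3A5 estimate as supplementary to the within-cohort results, and say that it assumes a common CYP3A5 effect. At 3/15 the interaction SE is 0.75 x sqrt(2 x (1/3+1/15)) = 0.671, a 95% half-width of about 1.37 log2, so 36 patients cannot check this well.

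**Cost.** SAP wording only, plus power if race has no effect: 93% falls to 82-83% at 3/15, 95% to 90% at 4/14 and 96% to 94% at 5/13. If the 2-fold effect exists in one cohort only, the pooled estimate averages 0.5 log2 with about 30% power at 3/15, so it must not replace the within-cohort tests. Labelling the stepwise AUC model exploratory would be a lighter step, but it would leave the wrong selection in place.
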